Abbreviations: anti-CCP-2, anti-cyclic citrullinated peptide-2; CBC, complete blood count; FSH, follicle-stimulating hormone; HIV, human immunodeficiency virus; HLA-DRB1, human leukocyte antigen Class II histocompatibility antigen, DRB1 beta chain; hsCRP, high-sensitivity C-reactive protein; IFN- γ , interferon gamma; IRT, Interactive Response Technology; PPD, purified protein derivative; RF, rheumatoid factor; TB, tuberculosis; WOCBP, women of childbearing potential.

^a Randomization must occur within 28 days of signing the informed consent form. Participants who experience delays may extend the screening period to 42 days (see [Section 6.4.1.2](#)). Rescreening is allowed (see [Section 6.4.1.3](#)).

^b Please see [Section 6.4.1.2 \(Extended Screening\)](#) for further information.

Table 2-2: On-treatment Procedural Outline (IM101863): Single-blind Treatment Period (SBTP)

Procedure	Day 1 (Rand.) Visit 1	Week 4 Visit 2 (± 3 days)	Week 8 Visit 3 (± 3 days)	Week 12 Visit 4 (± 3 days)	Week 16 Visit 5 (± 3 days)	Week 20 Visit 6 (± 3 days)	Week 24a/ ET Visit 7a (± 3 days)	Notes
		Day 29	Day 57	Day 85	Day 113	Day 141	Day 169 or ET	
Eligibility Assessments								
Inclusion/Exclusion Criteria	X							Review of inclusion/exclusion criteria that are relative to the Randomization day.
Tender (68)/Swollen (66) Joint Count	X							Must be performed by a blinded Clinical Assessor; to be performed prior to randomization (see Section 9.1.2).
Randomize Participant Using IRT	X							Contact of IRT is required to randomize the participant on Day 1 (see Section 7.2).
Safety Assessments								
Targeted Physical Examination	X	X	X	X	X	X	X	
Vital Signs	X	X	X	X	X	X	X	Body temperature, seated blood pressure, and heart rate.
Adverse Events Assessment	X	X	X	X	X	X	X	Causality assessments must be performed by a blinded Clinical Assessor.
Concomitant Medication Use	X	X	X	X	X	X	X	
Laboratory Tests								
Urine Pregnancy Test	X	X	X	X	X	X	X	WOCBP only; serum test if needed (see Section 9.4.7). Performed locally.
Hematology (CBC)	X	X	X		X		X	See Table 9.4.7-1 .
Blood Chemistry	X	X	X	X	X	X	X	See Table 9.4.7-1 .
hsCRP	X	X	X	X	X	X	X	

Table 2-2: On-treatment Procedural Outline (IM101863): Single-blind Treatment Period (SBTP)

Procedure	Day 1 (Rand.) Visit 1	Week 4 Visit 2 (± 3 days)	Week 8 Visit 3 (± 3 days)	Week 12 Visit 4 (± 3 days)	Week 16 Visit 5 (± 3 days)	Week 20 Visit 6 (± 3 days)	Week 24a/ ET Visit 7a (± 3 days)	Notes
		Day 29	Day 57	Day 85	Day 113	Day 141	Day 169 or ET	

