Procedure	Wk 24b V7b (± 3 Days)	Wk 28 V8 (± 7 Days)	Wk 32 V9 (± 7 Days)	Wk 36 V10 (± 7 Days)	Wk 40 V11 (± 7 Days)	Wk 44 V12 (± 7 Days)	Wk 48 V13 (± 7 Days)	Wk 52 V14 (± 7 Days)	Wk 60 V15 (± 7 Days)	Wk 68 V16 (± 7 Days)	Wk 76 V17 (± 7 Days)	Wk 84 V18 (± 7 Days)	Wk 92 V19 (± 7 Days)	Wk 104/ET V20 (± 7 Days)	Notes
	Day 169	Day 197	Day 225	Day 253	Day 281	Day 309	Day 337	Day 365	Day 421	Day 477	Day 533	Day 589	Day 645	Day 729	
Safety Assessments															
Targeted Physical Examination		X	X	X	X	X	X	X	X	X	X	X	X	X	
Vital Signs		X	X	X	X	X	X	X	X	X	X	X	X	X	Body temperature, seated blood pressure, and heart rate.
Concomitant Medication Use		X	X	X	X	X	X	X	X	X	X	X	X	X	
Adverse Events Assessment		X	X	X	X	X	X	X	X	X	X	X	X	X	Causality assessments must be performed by a blinded Clinical Assessor.
Laboratory Tests															
Urine Pregnancy Test		X	X	X	X	X	X	X	X	X	X	X	X	X	WOCBP only; serum test if needed (see Section 9.4.7). Performed locally.
Hematology (CBC)		X		X		X		X	X	X	X	X	X	X	
Blood Chemistry		X		X		X		X	X	X	X	X	X	X	
hsCRP		X	X	X	X	X	X	X	X	X	X	X	X	X	

Table 2-3: On-treatment Procedural Outline (IM101863): Open-label Treatment Period (OLTP)

Procedure	Wk 24b	Wk 28	Wk 32	Wk 36	Wk 40	Wk 44	Wk 48	Wk 52	Wk 60	Wk 68	Wk 76	Wk 84	Wk 92	Wk 104/ET	Notes
	V7b (± 3 Days)	V8 (± 7 Days)	V9 (± 7 Days)	V10 (± 7 Days)	V11 (± 7 Days)	V12 (± 7 Days)	V13 (± 7 Days)	V14 (± 7 Days)	V15 (± 7 Days)	V16 (± 7 Days)	V17 (± 7 Days)	V18 (± 7 Days)	V19 (± 7 Days)	V20 (± 7 Days)	
	Day 169	Day 197	Day 225	Day 253	Day 281	Day 309	Day 337	Day 365	Day 421	Day 477	Day 533	Day 589	Day 645	Day 729	
RF				X				X						X	See Section 9.8 .
Anti-CCP-2				X				X						X	See Section 9.8 .
Efficacy Assessments															
Tender (68)/Swollen (66) Joint Count		X	X	X	X	X	X	X	X	X	X	X	X	X	Must be performed by a blinded Clinical Assessor (see Section 9.1.2).
Participant Assessment of Pain		X	X	X	X	X	X	X	X	X	X	X	X	X	See Appendix 6 .
Participant Global Assessment of Disease Activity		X	X	X	X	X	X	X	X	X	X	X	X	X	See Appendix 5 .

Table 2-3: On-treatment Procedural Outline (IM101863): Open-label Treatment Period (OLTP)

Procedure	Wk 24b V7b (± 3 Days)	Wk 28 V8 (± 7 Days)	Wk 32 V9 (± 7 Days)	Wk 36 V10 (± 7 Days)	Wk 40 V11 (± 7 Days)	Wk 44 V12 (± 7 Days)	Wk 48 V13 (± 7 Days)	Wk 52 V14 (± 7 Days)	Wk 60 V15 (± 7 Days)	Wk 68 V16 (± 7 Days)	Wk 76 V17 (± 7 Days)	Wk 84 V18 (± 7 Days)	Wk 92 V19 (± 7 Days)	Wk 104/ET V20 (± 7 Days)	Notes

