	Day 169	Day 197	Day 225	Day 253	Day 281	Day 309	Day 337	Day 365	Day 421	Day 477	Day 533	Day 589	Day 645	Day 729	
Physician Global Assessment of Disease Activity		X	X	X	X	X	X	X	X	X	X	X	X	X	Must be performed by a blinded Clinical Assessor (see Section 9.1.1 and to Appendix 7).
Physical Function (HAQ-DI)		X	X	X	X	X	X	X	X	X	X	X	X	X	See Appendix 8 .
Quality of Life Scale (SF-36)								X						X	See Appendix 9 .
Work Productivity and Activity (WPAI-RA v2)								X						X	See Appendix 10 .
Fatigue (FACIT-F v4)								X						X	See Appendix 11 .
Duration of Morning Stiffness								X						X	See Appendix 12 .
Study Treatment Administration															
Contact IRT	X	X	X	X	X	X	X	X	X	X	X	X	X	X	Contact of IRT is required to dispense medication at each office visit.
Dispense Diary Cards	X	X	X	X	X	X	X	X	X	X	X	X	X	X	
Collect and Review Diary Cards		X	X	X	X	X	X	X	X	X	X	X	X	X	

Table 2-3: On-treatment Procedural Outline (IM101863): Open-label Treatment Period (OLTP)

Procedure	Wk 24b V7b (± 3 Days)	Wk 28 V8 (± 7 Days)	Wk 32 V9 (± 7 Days)	Wk 36 V10 (± 7 Days)	Wk 40 V11 (± 7 Days)	Wk 44 V12 (± 7 Days)	Wk 48 V13 (± 7 Days)	Wk 52 V14 (± 7 Days)	Wk 60 V15 (± 7 Days)	Wk 68 V16 (± 7 Days)	Wk 76 V17 (± 7 Days)	Wk 84 V18 (± 7 Days)	Wk 92 V19 (± 7 Days)	Wk 104/ET V20 (± 7 Days)	Notes
	Day 169	Day 197	Day 225	Day 253	Day 281	Day 309	Day 337	Day 365	Day 421	Day 477	Day 533	Day 589	Day 645	Day 729	
Dispense Urine Pregnancy Kits for WOCBP for Home Use Every 4 Weeks									X	X	X	X	X	X	Not applicable if serum pregnancy testing is required per local regulations.
Dosing of Weekly Abatacept	X	X	X	X	X	X	X	X	X	X	X	X	X	X	Abatacept must be self-administered weekly between visits. See Section 7.1 .
Dispense Abatacept Kits	X	X	X	X	X	X	X	X	X	X	X	X	X	X	See Section 7.2 .
Reconciliation of Abatacept Kits		X	X	X	X	X	X	X	X	X	X	X	X	X	

Abbreviations: anti-CCP-2, anti-cyclic citrullinated peptide-2; CBC, complete blood count; ET, early termination; FACIT-F, Functional Assessment of Chronic Illness Therapy - Fatigue; HAQ-DI, Health Assessment Questionnaire Disability Index; hsCRP, high-sensitivity C-reactive protein; IRT, Interactive Response Technology; [REDACTED] RF, rheumatoid factor; [REDACTED] SF-36, 36-item Short Form Survey; V, Visit; Wk, Week; WOCBP, women of childbearing potential; WPAI-RA, Work Productivity and Activity Impairment Questionnaire - Rheumatoid Arthritis.

Table 2-4: Post-treatment Follow-up Period (PTFUP; IM101863)

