Procedure	Week 12 FU V1 (± 10 days) ^a	Week 24 FU V2 (± 10 days) ^a	Notes
	Day 85	Day 169	
Safety Assessments			
Vital Signs	X	X	Body temperature, seated blood pressure, and heart rate.
Adverse Events Assessment	X	X	
Concomitant Medication Report	X	X	
Laboratory Assessments			
Urine Pregnancy Test	X	X	WOCBP only; serum test if needed (see Section 9.4.7). Performed locally.

Abbreviations: FU, Follow-up; OLTP, Open-label Treatment Period; PTFUP, Post-treatment Follow-up Period; SBTP, Single-blind Treatment Period; V, Visit; WOCBP, women of childbearing potential.

^a Visits only apply to participants who complete the study at Day 729 or discontinue study treatment during the SBTP or OLTP AND are not treated with abatacept as a post-study drug. The first day of the PTFUP is Day 729 for participants who complete the OLTP or the day of last study treatment for participants who discontinue study treatment during the SBTP or OLTP. Participants who complete the OLTP or discontinue at any time prior to completing the OLTP AND are treated with post-study abatacept, regardless of the source, will not need to complete the PTFUP. The follow-up visit should ideally be an in-person visit. If this is not possible, a telephone follow-up visit will be performed to confirm the results of the urine pregnancy test as well as adverse event and concomitant medication review. Vital signs will not be collected as part of a telephone follow-up phone visit.

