- k) Participant Rescreening: This study permits the rescreening of a participant who has discontinued the study as a pretreatment failure (ie, participant has not been randomized/has not been treated) and still meets all inclusion/exclusion criteria. If rescreened, the participant must be re-consented. Participants can only be rescreened once.

3) Age and Reproductive Status

a) Female Participants

- i) Females, ages ≥ 18 years or local age of majority.
- ii) Women who are not of childbearing potential are exempt from contraceptive requirements.
- iii) Women participants must have documented proof that they are not of childbearing potential.
- iv) WOCBP must have a negative highly sensitive serum or urine pregnancy test (minimum sensitivity 25 IU/L or equivalent units of human chorionic gonadotropin [HCG]) within 24 hours prior to the start of study treatment.
 - (1) If a urine test cannot be confirmed as negative (eg, an ambiguous result), a serum pregnancy test is required. In such cases, the participant must be excluded from participation if the serum pregnancy result is positive.
- v) Women must not be breastfeeding and must agree not to breastfeed during the study and for 100 days thereafter.
- vi) Additional requirements for pregnancy testing during and after study intervention are located in [Section 2](#), Schedule of Activities.
- vii) The investigator is responsible for review of medical history, menstrual history, and recent sexual activity to decrease the risk for inclusion of a woman with an early undetected pregnancy.
- viii) WOCBP must agree to follow instructions for method(s) of contraception defined in [Appendix 4](#) and as described below and included in the ICF.
- ix) WOCBP are permitted to use hormonal contraception methods (as described in [Appendix 4](#)).
- x) A female participant is eligible to participate if she is not pregnant or breastfeeding, and at least 1 of the following conditions applies:
 - (1) Is not a WOCBP
OR
 - (2) Is a WOCBP and using a contraceptive method that is highly effective (with a failure rate of $< 1\%$ per year), preferably with low user dependency (as described in [Appendix 4](#)) during the intervention period and for at least 70 days (5 half-lives of the study treatment), and agrees not to donate eggs (ova, oocytes) for the purpose of reproduction for the same time period.

b) Male Participants

- i) Males, ages ≥ 18 years or local age of majority.

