7.1.1 Abatacept Treatment

On Day 1, participants will self-administer abatacept 125 mg SC from a prefilled syringe. On Day 8, participants will self-administer abatacept 125 mg SC. Thereafter, participants will self-administer abatacept 125 mg SC once every 7 days, up to and including Week 103 (Day 722).

Participants randomized to adalimumab will switch to abatacept 125 mg SC weekly at Week 24 (Day 169).

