7.2 Method of Treatment Assignment

All participants will be centrally randomized using an IRT. Before the study is initiated, each user will receive log-in information and directions on how to access the IRT. Each participant will be assigned a unique participant number after signing the ICF. Participant numbers will be used on all participants' study information. Participant numbers will not be reassigned. The investigator or designee will register the participant for enrollment by following the enrollment procedures established by the Sponsor.

The following information is required for enrollment:

- Date that informed consent was obtained
- Year of birth
- Gender at birth

Once enrolled in IRT, enrolled participants who have met all eligibility criteria will be ready to be randomized through the IRT. The following information is required for participant randomization:

- Participant number
- Year of birth
- Gender at birth (female or male)
- SE status (positive or negative)

The exact procedures for using the IRT will be detailed in the IRT manual.

Study treatment will be dispensed at the study visits as listed in [Section 2](#) (Schedule of Activities). Sufficient drug will be dispensed at each visit to cover treatment until the next scheduled visit. These will be in intervals of 4, 8, or 12 weeks according to the visit schedule.

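### Table 2-3 starts 4-weekly home pregnancy kits at Week 60 instead of Week 52, so no kit is supplied for a Week 56 test

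*Combined protocol and SAP*

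**What the plan says.** The pregnancy-testing schedule is in the visit tables. Inclusion criterion 3.a.vi (Section 6.1) says "Additional requirements for pregnancy testing during and after study intervention are located in" Section 2, and Section 3.3 expects WOCBP to be tested throughout the study without giving an interval.

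- **Table 2-2 (single-blind period):** an office urine test at all seven visits, Day 1 to Week 24, each 4 weeks apart. The note reads "WOCBP only; serum test if needed (see Section 9.4.7). Performed locally".
- **Table 2-3 (open-label period), office test row:** a test at Weeks 28, 32, 36, 40, 44, 48 and 52, then at Weeks 60, 68, 76, 84, 92 and 104.
- **Table 2-3, kit row:** "Dispense Urine Pregnancy Kits for WOCBP for Home Use Every 4 Weeks". Cells are blank from Week 24b to Week 52 and marked at Weeks 60, 68, 76, 84, 92 and 104. The only stated exception is for places where local rules require serum testing.
- **Section 7.2, on study drug:** "Sufficient drug will be dispensed at each visit to cover treatment until the next scheduled visit" and "These will be in intervals of 4, 8, or 12 weeks according to the visit schedule".
- **Table 9.4.7-1, footnote a:** self-testing between visits is allowed where local rules permit it. A participant who becomes pregnant stops study treatment at once. The footnote does not supply a kit.

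**The concern.** Home kits are needed once visits stop being 4 weeks apart. That happens on leaving the Week 52 visit, because the next visit is Week 60. A kit for the first point between visits, Week 56, has to be handed out at Week 52 or earlier, and the row hands out none. WOCBP are tested every 4 weeks up to Week 52, and the kits restore that interval from Week 60. Nothing in the protocol explains a single 8-week break between them.

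The safeguard is against fetal exposure. During the break participants inject abatacept weekly and continue methotrexate. A longer interval means that a pregnancy can go unrecognised for longer before treatment is stopped.

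**Working it through.** **1. Is the row read correctly?** Table 2-3 has 14 visit columns: Weeks 24b, 28, 32, 36, 40, 44, 48, 52, 60, 68, 76, 84, 92 and 104. The kit row splits into 8 blank visit cells, then 6 marks, then its note in the Notes column. The marks fall at Weeks 60 to 104. Two other rows test the alignment:

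- The rheumatoid factor row, split the same way, gives Weeks 36, 52 and 104. This matches the open-label sampling times in the separate Table 9.8.2-1.
- The SF-36 row gives Weeks 52 and 104.

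A column shift in the extracted text is therefore unlikely.

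**2. Which 4-weekly points have a test?** Weeks 0 to 104 in steps of 4 give 104/4 + 1 = 27 points. Office tests cover 7 (Table 2-2) + 13 (Table 2-3) = 20. The other 27 − 20 = 7 need a home kit from the preceding visit:

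| Point between visits | Preceding visit | Kit dispensed there? |
|---|---|---|
| Week 56 | Week 52 | No |
| Week 64 | Week 60 | Yes |
| Week 72 | Week 68 | Yes |
| Week 80 | Week 76 | Yes |
| Week 88 | Week 84 | Yes |
| Weeks 96 and 100 | Week 92 | Yes, if two tests are supplied |

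Six of the seven home points are supplied, so coverage is 20 + 6 = 26 of 27. If each mark means a single test, Week 100 is also missing and coverage is 25 of 27.

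**3. Length of the gap.** Week 52 is Day 365 and Week 60 is Day 421, each ± 7 days.

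- Nominal: 421 − 365 = 56 days, against 28.
- Shortest: 414 − 372 = 42 days.
- Longest: 428 − 358 = 70 days.

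**4. Doses before the next test.** Under Section 7.1.1, weekly doses fall on Day 1 + 7k. Week 56 is Day 1 + 7 × 56 = Day 393. Doses from then until the Week 60 test on Day 421 fall on Days 393, 400, 407 and 414, which is 4 doses. A Week 60 visit on Day 414 gives 3 and one on Day 428 gives 5, because dosing follows assessments on visit days.

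**5. Expected pregnancies in the 28 affected days.** The protocol does not give the number of WOCBP, so N is an assumption. The rate is the 1% per year ceiling for highly effective contraception (criterion 3.a.x). The formula is N × 0.01 × 28/365.

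- N = 75: 0.06.
- N = 225: 0.17.
- N = 300 (all participants): 0.23.

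N = 300 is a ceiling and not realistic. Section 3 says women are 2 to 3 times as likely as men to develop the disease. On that ratio about 200 (300 × 2/3) to 225 (300 × 3/4) of 300 would be women, before removing those past childbearing age and those off treatment by Week 52. Appendix 4 notes that typical-use failure rates may differ from the ceiling.

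**The case against.** The strongest counter-argument is that no sentence requires a Week 56 test. The 4-weekly interval after Week 52 appears only in the label of a dispensing row, which could mean how to use kits once they are issued from Week 60. On that reading the schedule requires tests at Weeks 52 and 60, and both are there. Nor is testing 4-weekly everywhere: follow-up tests after the last dose are 12 weeks apart (Table 2-4). It is true that Week 56 is inferred. But the row has no purpose other than covering gaps between visits, the first gap is as long as the four that follow it, and no reason is given for leaving it open.

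Four narrower points stand as qualifications:

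- The count of 26 of 27, and the claim that this is the only break on treatment, depend on Week 92 supplying two tests. The plural in the label supports this, but no quantity is stated.
- The upper pregnancy figure of 0.23 is implausibly high, as shown above.
- A pregnancy could come to light before Week 60 by other means, since self-testing between visits is allowed. The 4-week delay is therefore what the schedule permits and need not occur.
- The protocol does not say what the Week 104 kits are for.

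**Conclusion.** The inconsistency is real and minor. At sites using home urine testing, the schedule leaves one 56-day interval between pregnancy tests (42 to 70 with windows) where the row label implies 28, and up to 4 additional abatacept doses (3 to 5) could follow a pregnancy detectable at Week 56. This rests on reading the row label as the intended interval from Week 52 onward and, for the claim that Week 56 is the only gap, on two tests being supplied at Week 92.

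The consequence is limited. The gap occurs once, office tests sit on both sides of it, and highly effective contraception is required. It does not arise where local rules require serum testing or do not permit home testing. On the assumed numbers, well under one pregnancy would fall in the affected 28 days. Sample size, endpoints and analyses are unaffected.

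**What to change.** Add an X at Week 52 in the kit row of Table 2-3. All seven points between visits are then supplied, again taking Week 92 to provide two tests; a short entry in the Notes column could state that quantity.

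Add the mark instead of moving the whole row one column to the left, which would remove the Week 104 mark. Table 2-4, footnote a, says that where an in-person follow-up is not possible "a telephone follow-up visit will be performed to confirm the results of the urine pregnancy test", and a kit handed out at Week 104 could serve that test. The protocol does not state this link, but keeping the mark preserves the option.

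The cost is one kit per applicable participant at an existing visit, and one table cell at the next amendment. Visits, sample size and analysis do not change.

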3 INTRODUCTION

Rheumatoid arthritis (RA) is the most common chronic inflammatory arthritis, affecting approximately 1% of the population worldwide.¹ It is a complex and progressive disease with several heterogeneous aspects, including clinical presentation, detectable serological biomarkers, genetic risk factors, and speed of disease progression.^{2,3,4,5} Women are 2 to 3 times more likely to develop the disease as compared with men, with a peak incidence between the fourth and sixth decades of life.^{6,7,8,9} The etiology of RA involves genetic and epigenetic components, as well as environmental stimuli, such as cigarette smoking, dust exposure, and the microbiome, which represents an “internal” environment.¹⁰ The natural history of RA is characterized by joint destruction, impaired physical function, and poor health-related quality of life. Joint erosions can be seen within 6 months of disease onset in the majority of patients and occur more rapidly in the first year compared with later disease.¹¹ Radiographic evidence of joint damage can be difficult to detect in early RA but has been shown to progress in a linear manner after the first year, and there is little evidence that current therapies can reverse the structural damage once it occurs.¹²

The underlying pathophysiology of RA involves an interplay between the adaptive and innate immune systems. Several environmental and genetic factors are prominent risks for the development and clinical course of RA.⁴ The role of genetics in RA was first identified by researchers who noted that lymphocytes from RA patients were less likely to stimulate lymphocytes from other unrelated RA patients in mixed lymphocyte cultures.¹³ The genetic basis of this was later identified as being due to the high frequency of related human leukocyte antigen Class II histocompatibility antigen, DRB1 beta chain (*HLA-DRB1*) locus alleles among RA patients, a major histocompatibility complex Class II protein receptor. These *HLA-DRB1* alleles encode for a common amino acid motif in codon positions 70-74. Together these alleles are referred to as the shared epitope (SE), and they increase the risk of developing, and the severity of, RA.¹⁴ While the specific *HLA-DRB1* risk allele present shows regional variability, they all share the same amino acid motif of the SE, indicating the SE is a genetic risk shared across human populations.¹⁵

Abnormalities in the cellular and humoral immune response in RA drive the production of autoantibodies (such as rheumatoid factor [RF] and anti-citrullinated protein antibodies [ACPA]) that define “seropositive” RA. Of all RA patients, approximately 70-90% are ACPA-positive (ACPA+), 60-80% are RF-positive (RF+), and ~70% are seropositive for both ACPA and RF.^{3,16} Seropositivity drives a severe disease subtype of RA because autoantibodies such as ACPA and RF are directly involved in the inflammatory response that is a key driver of disease pathophysiology.¹⁷ The presence of autoantibodies in RA is associated with increased disease activity, systemic manifestations, and joint damage.^{17,18,19,20} One of the most significant genetic risk factors for ACPA+ RA is the SE, and 70-80% of ACPA+ RA patients are SE-positive (SE+; see [Section 9.8.1](#) for definition of SE positivity).^{4,21,22,23} At diagnosis, ACPA+ and ACPA-negative (ACPA-) RA patients have similar clinical presentations, but as they progress, ACPA+ patients experience more extensive radiological destruction.²⁴ As compared with ACPA

seropositivity, RF serostatus has a similar but less severe impact on progressive bone erosion.⁵ Based on real-world data analysis of the Brigham and Women's Rheumatoid Arthritis Sequential Study (BRASS) registry, ACPA seropositivity is associated with reduced likelihood of disease remission.²⁵ In addition to articular disease, seropositivity is also associated with higher rates of developing various systemic manifestations, including lung involvement and cardiovascular disease, that contribute to increased morbidity and mortality of RA patients.^{18,19,20,26,27,28,29,30,31,32} Consequently, seropositive RA is associated with a greater economic burden, as evidenced by a 46% higher RA-related cost as compared with seronegative RA, based on a retrospective analysis of United States (US) claims data.³³

In general, treatment options for RA patients range from agents that provide symptomatic relief (eg, analgesics, nonsteroidal anti-inflammatory drugs [NSAIDs]), to corticosteroids and disease-modifying antirheumatic drugs [DMARDs] that affect long-term structural damage. The approach to RA treatment involves early intervention and progressive changes in therapy to improve signs and symptoms and to prevent long-term structural damage. Traditionally, patients who are early in the disease course initiate treatment with 1 or more conventional synthetic DMARDs (eg, methotrexate [MTX]). Early intervention appears to offer the best opportunity for achieving favorable outcomes, such as induction of clinical remission, prevention of long-term joint damage, and restoration of normal physical function in patients with early RA.^{34,35,36,37,38,39} If there is an inadequate response to conventional synthetic DMARDs, these patients may be candidates for biologic therapy. The treatment paradigm for treating RA patients has been shifting to the early use of combination therapy with both conventional and biologic DMARDs, which has been shown to result in more favorable outcomes.⁴⁰

Commercially available biologic agents for RA have been shown to improve the signs and symptoms of RA and decrease the progression of structural damage in patients who have had an inadequate response to at least 1 DMARD, and in patients with severe, active, and progressive disease not previously treated with DMARDs. Consistent with the principle of early treatment with combination therapy, use of these biologic agents is becoming increasingly frequent in patients with factors predictive of rapidly progressive disease, such as early radiographic erosion and positive autoantibodies, such as RF and ACPA, which have been shown to be predictive of severe erosive disease. Guidelines from organizations such as the French Society of Rheumatologists Working Group for Therapeutic Strategies for Rheumatoid Arthritis (Strategies Therapeutiques de la Polyarthrite Rhumatoïde [STPR]) and others, specifically recommend the very early use of biologic therapy in patients with poor prognostic factors, taking into account the benefit-risk profile of the different therapeutic options.

Tumor necrosis factor (TNF) antagonists, which are the most commonly prescribed biologics for RA, have demonstrated consistent and favorable benefit-risk profiles; however, many patients do not achieve an adequate response or complete control of inflammation. In those who do achieve a response, prolonged maintenance of response is difficult. In addition, there are important safety concerns associated with TNF antagonists and other biologic agents. As clinical practice shifts to the earlier use of biologics, it is anticipated that patients will be treated with biologic therapies for

a longer duration over the course of their disease. As such, the availability of a treatment option with prolonged maintenance of efficacy and a favorable long-term safety profile, such as abatacept, would be highly desirable for these patients.

Abatacept is a selective costimulation modulator that blocks the interaction between cluster of differentiation (CD) 80/CD86 on antigen-presenting cells and CD28 on T cells.⁴¹ This interaction provides a key signal necessary for full activation of T cells. Activated T cells play an important role in the pathogenesis of RA, especially early in the disease process, by participating in the autoimmune cascade that leads to joint inflammation and destruction. It is hypothesized that autoreactive T cells may be central to this process by producing proinflammatory cytokines and providing help to B cells, leading to the production of autoantibodies, which in turn contribute to downstream inflammatory events, including the recruitment of neutrophils, elaboration of cytokines such as TNF-alpha, synovitis, and ultimately joint destruction.⁴² By inhibiting CD28-mediated immune activation, abatacept blocks antigen recognition and modulates the immune response to decrease T-cell activation and antibody production. Therefore, abatacept interferes with a step hypothesized to be early in the pathogenesis of RA.

Intravenously (IV) administered abatacept was first approved in the US for the treatment of moderate-to-severe RA in adults in Dec-2005. Since then, IV abatacept has received marketing approval for the treatment of adult RA in many other countries, including the European Union (EU), Japan, Latin America, and other countries.⁴¹

The subcutaneous (SC) formulation of abatacept was first approved in the US for the treatment of moderate-to-severe RA in adults in Jul-2011. Abatacept SC has subsequently received marketing approval for the treatment of adult RA in the EU and other regions of the world.⁴¹

The IM101235 (Abatacept vs adalimumab comparison in biologic-naïve RA participants with background methotrexate [AMPLE]; ClinicalTrials.gov: NCT00929864)⁴³ study compared the efficacy of abatacept (125 mg weekly) and TNF-alpha blockade (adalimumab, 40 mg biweekly), both in combination with MTX, in adult participants with RA for 5 or fewer years who had an inadequate response to MTX (methotrexate inadequate responders [MTX-IR]) but who were naïve to a biologic DMARDs. The primary endpoint was met, demonstrating that abatacept was noninferior to adalimumab based on the proportion of participants who achieved a 20% improvement in American College of Rheumatology criteria (ACR20) at 1 year. In addition, ACR20 response rates in both treatment groups increased comparably over the 12-month treatment period.

The IM101567 (Early AMPLE; ClinicalTrials.gov: NCT02557100)⁴⁴ trial was a mechanistic head-to-head study assessing changes in the immune profile with abatacept (125 mg weekly) and TNF-alpha blockade (adalimumab, 40 mg biweekly), both in combination with MTX, in 80 adult participants with early RA (symptoms for ≤ 12 months) who had an inadequate response to MTX. Although this exploratory study did not have any primary or secondary endpoints, numerically higher American College of Rheumatology (ACR) responses were seen with abatacept vs adalimumab after 24 weeks of treatment. The study also prospectively explored the relationship

between clinical efficacy and the presence of *HLA-DRB1* risk alleles (ie, SE). The vast majority of participants randomized in the Early AMPLE study were SE+ and showed higher differential efficacy (ACR responses and Disease Activity Score 28-joint count calculated using C-reactive protein [DAS28-CRP] remission) to abatacept vs adalimumab compared with the overall population, indicating that the differential benefit to therapy with abatacept in this population is driven by the SE+ patient subgroup.

In order to confirm the exploratory observations in Early AMPLE relating to abatacept efficacy in SE+ participants, IM101863 aims to demonstrate the superiority in efficacy of abatacept compared with adalimumab in a population of RA participants characterized by early disease, MTX-IR, and seropositivity (RF+ and ACPA+) and expressing SE HLA Class II risk alleles (ie, SE+).

